7.2.2 Permanent Product Measurement of Performance (PERMP)

The PERMP is a 5 page math test consisting of 80 problems per page (total of 400 problems). Both attempted problems and correct problems will be assessed. Subjects are to complete as many problems as possible in 10 minutes. The appropriate math level for each subject is determined based on results of a math pretest administered at screening (Visit 2). Performance is measured by the number of math problems attempted (PERMP-A) and the number of math problems correctly completed (PERMP-C). Like the SKAMP, the PERMP will be administered as a practice at Visit 2 and as the final tests at Visits 4 (Day 1) and 5 (Day 15), during each of 7 class sessions occurring at 8:00 am, 10:00 am, 12:00 pm, 2:00 pm, 4:00 pm, 6:00 pm, and 8:00 pm of the laboratory classroom days. In this study, the change from baseline at Day 15 in PERMP-A and PERMP-C scores at each of the post-dose assessment times and the PERMP-A and PERMP-C scores at each of the post-dose assessment times on Day 15 are defined as secondary efficacy measures. Higher PERMP scores signify higher performance and less severe ADHD symptoms. Therefore, increases in PERMP scores over time will indicate improvement of symptoms, while decreases in PERMP scores over time will indicate worsening of symptoms.

No imputation for missing PERMP values will be performed.

7.3 Eligibility Criteria and ADHD Symptom Control Assessments

7.3.1 Schedule for Affective Disorders and Schizophrenia for School-Age Children Present and Lifetime version (K-SADS-PL)

The K-SADS-PL is used at screening to confirm the diagnosis of ADHD.

The K-SADS-PL is a semi-structured diagnostic interview designed to assess current and past episodes of psychopathology in children and adolescents according to Diagnostic and Statistical Manual for Mental Disorders Fourth Edition; Text Revision (DSM-IV-TR) criteria. The K-SADS-PL covers a broad spectrum of most child psychiatric diagnoses, with the exception of pervasive development disorders and personality disorders. The K-SADS-PL includes questions about school performance and other issues relevant to children and adolescents. There is a base instrument (82 items) and 5 required diagnostic supplements which are completed depending on the results of the base screening: (1) Affective Disorders; (2) Psychotic Disorders; (3) Anxiety Disorders; (4) Behavioral Disorders; (5) Substance Abuse and Other Disorders.

7.3.2 ADHD Rating Scale Version IV - Home Version (modified for investigator administration) (ADHD-RS-IV HV)

The ADHD-RS-IV HV is used to assess clinical worsening on Day -1.

The ADHD-RS-IV HV was developed to measure the behaviors of children with ADHD. The ADHD-RS-IV HV is a validated scale that consists of 18 items designed to reflect current symptomatology of ADHD based on Diagnostic and Statistical Manual for Mental Disorders Fourth Edition; Text Revision (DSM-IV-TR) criteria and is also consistent with DSM-5 criteria. Each item is scored from a range of zero (reflecting no symptoms) to 3 (reflecting severe symptoms) with total scores ranging from zero to 54. Higher ADHD-RS-IV HV total scores signify greater severity in ADHD symptoms.

The following ADHD-RS-IV HV scores will be assessed:

- ADHD-RS Total score (all items).
- ADHD-RS Hyperactivity/Impulsivity subscale score (even number items 2 through 18).
- ADHD-RS Inattentiveness subscale score (odd number items 1 through 17).

No imputation for missing ADHD-RS data will be performed. Descriptive statistics for the ADHD-RS-IV HV scores will be presented for each time point and data will also be presented in a listing.

7.4 Efficacy Outcomes

7.4.1 Primary Efficacy Outcome

The primary efficacy outcome is the change from baseline (Visit 4) at Day 15 (Visit 5) in ADHD symptoms as measured by mean SKAMP-CS obtained from an average of the 7 assessments collected across the 12 hour classroom day (12 to 24 hours post-dose).

7.4.2 Secondary Efficacy Outcomes

Secondary efficacy outcomes include:

- Mean SKAMP-Combined score from the 7 assessments collected across the 12-hour classroom day (12 to 24 hours post-dose) on Day 15
- SKAMP-Combined score at each of the assessment times (12-, 14-, 16-, 18-, 20-, 22-, and 24-hours post-dose) during the classroom day on Day 15
- Change from baseline at Day 15 in SKAMP-Combined score at each of the assessment times (12-, 14-, 16-, 18-, 20-, 22-, and 24-hours post-dose) during the classroom day
- Change from baseline at Day 15 in mean SKAMP-Attention subscale score obtained from the 7 assessments collected across the 12-hour classroom day (12 to 24 hours post-dose)
- SKAMP-Attention subscale score at each of the assessment times (12-, 14-, 16-, 18-, 20-, 22-, and 24-hours post-dose) during the classroom day on Day 15
- Change from baseline at Day 15 in SKAMP-Attention subscale score at each of the assessment times (12-, 14-, 16-, 18-, 20-, 22-, and 24-hours post-dose) during the classroom day
- Change from baseline at Day 15 in mean SKAMP-Depoerty subscale score obtained from the 7 assessments collected across the 12-hour classroom day (12 to 24 hours post-dose)
- SKAMP-Depoerty subscale score at each of the assessment times (12-, 14-, 16-, 18-, 20-, 22-, and 24-hours post-dose) during the classroom day on Day 15
- Change from baseline at Day 15 in SKAMP-Depoerty subscale score at each of the assessment times (12-, 14-, 16-, 18-, 20-, 22-, and 24-hours post-dose) during the classroom day

- Change from baseline at Day 15 in Permanent Product Measure of Performance (PERMP)-Attempted and Correct Problems scores at each of the assessment times (12-, 14-, 16-, 18-, 20-, 22-, and 24-hours post-dose) during the classroom day
- PERMP-Attempted and Correct Problems scores at each of the assessment times (12-, 14-, 16-, 18-, 20-, 22-, and 24-hours post-dose) during the classroom day on Day 15

7.5 Analysis Methods

7.5.1 Primary Efficacy Analyses

The primary efficacy analysis will be performed on the ITT population. The primary efficacy outcome is the change from baseline (Visit 4) at Day 15 (Visit 5) in ADHD symptoms as measured by mean SKAMP-CS obtained from an average of the 7 assessments collected across the 12 hour classroom day (12 to 24 hours post-dose).

The key elements of the primary efficacy analysis are as follows:

Data: Change from baseline at Day 15 of mean SKAMP-CS measured on the laboratory classroom days, Visits 4 (baseline) and 5 (Day 15). This will be measured by taking the mean across all 7 assessment time points (8:00 am, 10:00 am, 12:00 pm, 2:00 pm, 4:00 pm, 6:00 pm, and 8:00 pm) both at baseline and at Day 15. The mean SKAMP-CS will not be rounded prior to analysis. Missing individual item data will first be imputed as described in Section 7.1.1.1 before taking the mean across all assessment time points.

Model: ANCOVA

Fixed effects: The following fixed effects are planned:

- Treatment
- Mean SKAMP-CS at baseline (Visit 4)
- Site

The null hypothesis:

H_0 : Change from baseline at Day 15 of the mean SKAMP-CS over all time points from 8:00 am to 8:00 pm on the laboratory classroom days are the same for dasotraline 4 mg/day and placebo

will be tested against the 2-sided alternative hypothesis:

H_1 : Change from baseline at Day 15 of the mean SKAMP-CS over all time points from 8:00 am to 8:00 pm on the laboratory classroom days are not the same for dasotraline 4 mg/day and placebo.

The average treatment difference over all post-dose time points will be estimated using LS means from the ANCOVA. The treatment comparison will be conducted as a 2-sided test at the 5% level of significance. The standard error and 95% confidence interval for the treatment difference as well as the treatment effect size will be provided. Effect size will be calculated as the LS mean treatment difference divided by the observed pooled standard deviation.

The primary efficacy analysis will also be repeated for the per protocol (PP) population.

7.5.2 Secondary Efficacy Analyses

The secondary efficacy outcomes include:

- Mean SKAMP-Combined score from the 7 assessments collected across the 12-hour classroom day (12 to 24 hours post-dose) on Day 15
- SKAMP-Combined score at each of the assessment times (12-, 14-, 16-, 18-, 20-, 22-, and 24-hours post-dose) during the classroom day on Day 15
- Change from baseline at Day 15 in SKAMP-Combined score at each of the assessment times (12-, 14-, 16-, 18-, 20-, 22-, and 24-hours post-dose) during the classroom day
- Change from baseline at Day 15 in mean SKAMP-Attention subscale score obtained from the 7 assessments collected across the 12-hour classroom day (12 to 24 hours post-dose)
- SKAMP-Attention subscale score at each of the assessment times (12-, 14-, 16-, 18-, 20-, 22-, and 24-hours post-dose) during the classroom day on Day 15
- Change from baseline at Day 15 in SKAMP-Attention subscale score at each of the assessment times (12-, 14-, 16-, 18-, 20-, 22-, and 24-hours post-dose) during the classroom day
- Change from baseline at Day 15 in mean SKAMP-Deportment subscale score obtained from the 7 assessments collected across the 12-hour classroom day (12 to 24 hours post-dose)

- SKAMP-Depoerty subscale score at each of the assessment times (12-, 14-, 16-, 18-, 20-, 22-, and 24-hours post-dose) during the classroom day on Day 15
- Change from baseline at Day 15 in SKAMP-Depoerty subscale score at each of the assessment times (12-, 14-, 16-, 18-, 20-, 22-, and 24-hours post-dose) during the classroom day
- Change from baseline at Day 15 in Permanent Product Measure of Performance (PERMP)-Attempted and Correct Problems scores at each of the assessment times (12-, 14-, 16-, 18-, 20-, 22-, and 24-hours post-dose) during the classroom day
- PERMP-Attempted and Correct Problems scores at each of the assessment times (12-, 14-, 16-, 18-, 20-, 22-, and 24-hours post-dose) during the classroom day on Day 15

Descriptive statistics for the SKAMP-CS, SKAMP-Attention subscale scores, SKAMP-Depoerty subscale scores, PERMP-A and PERMP-C scores will be calculated for the change from baseline (Visit 4) at Day 15 (Visit 5), average across all time points and for each time point individually for the laboratory classroom day on Day 15, and will be presented for each treatment as well for the differences between the treatments (dasotraline 4 mg/day vs. placebo) based on the ITT population.

In addition, the secondary SKAMP and PERMP efficacy variables will be analyzed based on the same ANCOVA model as described above for the ITT population.

The observed means, LS means and associated standard error bars will be plotted over time for SKAMP-CS and the PERMP scores for the laboratory classroom day at Baseline (Visit 4) and Day 15 (Visit 5) by treatment group. Change from baseline SKAMP-CS, change from baseline SKAMP subscale scores, and change from baseline PERMP scores will be plotted over time at Day 15 (Visit 5) by treatment group. Change from baseline SKAMP-CS will also be plotted over time at Day 15 (Visit 5) by subgroup (age, gender, race).

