15.3.5.2. Secondary Efficacy Endpoint Analysis

A similar ANCOVA model, as described above, will be used for the secondary efficacy endpoints for the ITT population.

- Change from baseline at Day 15 in SKAMP-Combined score at each of the assessment times (12-, 14-, 16-, 18-, 20-, 22-, and 24-hours postdose) during the classroom day
- Change from baseline at Day 15 in mean SKAMP-Attention subscale score obtained from the 7 assessments collected across the 12 hour classroom day (12 to 24 hours postdose)
- Change from baseline at Day 15 in SKAMP-Attention subscale score at each of the assessment times (12-, 14-, 16-, 18-, 20-, 22-, and 24-hours postdose) during the classroom day
- Change from baseline at Day 15 in mean SKAMP-Deportment subscale score obtained from the 7 assessments collected across the 12 hour classroom day (12 to 24 hours postdose)
- Change from baseline at Day 15 in SKAMP-Deportment subscale score at each of the assessment times (12-, 14-, 16-, 18-, 20-, 22-, and 24-hours postdose) during the classroom day
- Change from baseline at Day 15 in PERMP-Attempted and Correct Problems scores at each of the assessment times (12-, 14-, 16-, 18-, 20-, 22-, and 24-hours postdose) during the classroom day
- Mean SKAMP-Combined score from the 7 assessments collected across the 12 hour classroom day (12 to 24 hours postdose) on Day 15
- SKAMP-Combined score at each of the assessment times (12-, 14-, 16-, 18-, 20-, 22-, and 24-hours postdose) during the classroom day on Day 15
- SKAMP-Attention subscale score at each of the assessment times (12-, 14-, 16-, 18-, 20-, 22-, and 24-hours postdose) during the classroom day on Day 15
- SKAMP-Deportment subscale score at each of the assessment times (12-, 14-, 16-, 18-, 20-, 22-, and 24-hours postdose) during the classroom day on Day 15
- PERMP-Attempted and Correct Problems scores at each of the assessment times (12-, 14-, 16-, 18-, 20-, 22-, and 24-hours postdose) during the classroom day on Day 15

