1. PURPOSE OF THE STATISTICAL ANALYSIS PLAN

The purpose of the analyses described in this document is to compare the safety and efficacy of dasotraline to placebo in pediatric patients with attention deficit hyperactivity disorder (ADHD).

The statistical analysis plan (SAP) is written with due consideration of the recommendations outlined in the most recent International Conference on Harmonisation (ICH) E9 Guideline entitled Guidance for Industry: Statistical Principles for Clinical Trials [1] and the most recent ICH E3 Guideline, entitled Guidance for Industry: Structure and Content of Clinical Study Reports [2].

This SAP describes the populations that will be analyzed, the subject characteristics parameters, the efficacy parameters, and the safety parameters. The details of the specific statistical methods that will be used will be provided. If additional analyses are required to supplement the planned analyses described in this SAP, they may be completed and will be identified in the clinical study report (CSR). [Table](#), [figure](#), and [listing](#) specifications are provided in separate documents.

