12.2 Changes in the Analysis Planned in the Protocol

No changes are planned as of the date of the SAP.

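### As written, SAP 7.5.2 adjusts the PERMP and SKAMP-subscale endpoints for baseline mean SKAMP-CS instead of their own baseline, at a cost in precision that depends on undocumented correlations

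*SAP*

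**What the plan says.** SAP 7.5.1 specifies the primary ANCOVA with three terms: treatment, site, and a covariate listed as "Mean SKAMP-CS at baseline (Visit 4"). For the primary endpoint that covariate is the endpoint's own baseline.

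SAP 7.5.2 lists the secondary outcomes and then says that "the secondary SKAMP and PERMP efficacy variables will be analyzed based on the same ANCOVA model as described above for the ITT population". It names no other covariate for PERMP or for the Attention and Deportment subscales. It also plans a display: "The observed means, LS means and associated standard error bars will be plotted over time for SKAMP-CS and the PERMP scores".

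Protocol 15.3.5.2 is looser: "A similar ANCOVA model, as described above, will be used for the secondary efficacy endpoints for the ITT population". SAP 12.2 reports no departure from the protocol analysis: "No changes are planned as of the date of the SAP". SAP section 1 says that table, figure and listing "specifications are provided in separate documents", which are not available here.

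A PERMP baseline exists. SAP 7.2.2 has the test given "as the final tests at Visits 4 (Day 1) and 5 (Day 15), during each of 7 class sessions". The same section adds: "No imputation for missing PERMP values will be performed".

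**The concern.** The covariate suits the primary endpoint because it is that endpoint's baseline. Carried over unchanged, it adjusts a count of math problems for an observer's behaviour rating, although the same math test was given seven times on Day 1. It also adjusts each subscale for the total score.

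The hourly comparisons serve the secondary objective of effect across 12 to 24 hours postdose (Protocol 5.2), and the PERMP least-squares means are to be plotted with standard error bars. A covariate that explains less of the outcome variance widens those bars and lowers power. The protocol says *similar* and the SAP says *same*, so two programmers could fit different models and both claim to follow the plan. SAP section 10 reuses the 7.5 methods for the exploratory 6 mg/day arm of about 20 subjects, which inherits the gap.

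**Working it through.** **Stated figures.** The documents give no precision figure for any secondary endpoint. Their one related figure, at least 95% power for the primary endpoint (50 per arm, difference 4.0, SD 5, two-sided 5%), reproduces at 97.7% by the two-sample t-test and is not affected.

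**Counts (SAP 7.5.2).**
- SKAMP-CS: 1 Day 15 mean + 7 Day 15 hourly + 7 hourly change = 15. These already use the Day 1 mean of their own measure.
- Subscales: 2 × (1 mean change + 7 Day 15 hourly + 7 hourly change) = 30.
- PERMP: 2 × (7 Day 15 hourly + 7 hourly change) = 28.
- Total 73. Not own-measure: 30 + 28 = 58, of which 28 are absolute Day 15 scores (14 + 14) and 30 are changes (14 + 14 + 2).

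**Assumptions.** All correlations below are assumed. Scores have unit variance on both days, and baseline SKAMP-CS correlates equally with the measure on Day 1 and Day 15. Results are ratios of standard errors, as written over own-baseline.

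**Day 15 PERMP against its Day 1 mean.** Ratio = sqrt((1 − r²)/(1 − ρ²)), with r the SKAMP-PERMP correlation and ρ the correlation of the Day 15 score with its Day 1 mean.
- r = -0.3: ρ = 0.5 gives sqrt(0.91/0.75) = 1.10; ρ = 0.7 gives sqrt(0.91/0.51) = 1.34.
- r = -0.5: ρ = 0.5 gives sqrt(0.75/0.75) = 1.00; ρ = 0.7 gives sqrt(0.75/0.51) = 1.21.

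A comparison with 90% power under the own-baseline model would have about 84%, 76% and 68% when its standard error is 10%, 21% and 34% larger.

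**Hourly structure.** Let w be the correlation between two sessions on one day, c the correlation across days, and m = (1 + 6w)/7 the variance of the seven-session mean. Then ρ = c/√m. Let k be the correlation between subscale and SKAMP-CS Day 1 means.

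| w, c | ρ | PERMP Day 15 vs Day 1 mean, r = -0.3 | PERMP change vs Day 1 mean | PERMP change vs time-matched | Subscale Day 15 vs Day 1 mean, k = 0.9 |
|---|---|---|---|---|---|
| 0.6, 0.5 | 0.62 | 1.21 | 1.02 | 1.15 | 1.06 |
| 0.7, 0.6 | 0.70 | 1.33 | 1.02 | 1.12 | 1.09 |
| 0.8, 0.7 | 0.77 | 1.49 | 1.02 | 1.08 | 1.13 |
| 0.9, 0.8 | 0.84 | 1.74 | 1.02 | 1.05 | 1.20 |

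Formulas for residual variance:
- PERMP change: as written 2(1 − c); Day 1 mean 2(1 − c) − (c − m)²/m; time-matched 1 − c².
- Subscale Day 15: as written 1 − k²c²/m; Day 1 mean 1 − c²/m.

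First row, with m = 4.6/7 = 0.657:
- PERMP change against the Day 1 mean: sqrt(1.000/0.962) = 1.02.
- PERMP change against time-matched: sqrt(1.000/0.750) = 1.15.
- Subscale Day 15: sqrt(0.692/0.620) = 1.06.

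Other subscale results, against the Day 1 mean:
- Day 15 scores with k = 0.7: 1.15 to 1.48.
- Hourly change, k from 0.7 to 0.9: 1.01 or less.
- The two mean changes: sqrt((2(1 − ρ) − (k(1 − ρ))²)/(1 − ρ²)), with ρ here the correlation between the two day means, is about 1.01 to 1.08 for k from 0.7 to 0.9 and ρ from 0.5 to 0.9.

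**Where the loss falls.** For PERMP with r = -0.3:
- Against the Day 1 mean, at w = 0.5, c = 0.3 (ρ = 0.40), absolute scores lose 4% and change scores 5%. Above that, absolute scores lose more.
- Against a time-matched baseline, at c = 0.5, absolute scores lose sqrt(0.91/0.75) = 10% and change scores 15%. The order reverses at c = (1 + r²)/2 = 0.55. It reverses at 0.5 if SKAMP-CS relates to Day 15 only through the measure's own baseline.

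**Simulation.** With 50 per arm, 5 sites and r = -0.3, 3,000 simulated trials gave Day 15 PERMP ratios of 1.21, 1.33, 1.49 and 1.74 and change ratios of 1.02. Mean estimates were within 0.004 SD of zero under no effect.

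**The case against.** **It may be only wording.** The SAP says *based on* the model, the protocol says *similar*, SAP 12.2 declares no change, and in the primary model the covariate is the endpoint's own baseline. Carrying that principle over is a natural reading, and the separate table specifications may state it. This stands as a statement about likely intent. It does not supply the missing text: the only covariate named is mean SKAMP-CS.

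**The subscale loss can be small.** SKAMP-CS contains the subscale items. With k = 0.9, the covariate as written does slightly better for Day 15 subscale scores than a time-matched own baseline in the first two rows of the table (4% and 3% smaller standard error). This stands, and it is why the Day 1 mean is the better replacement there. The value of k also depends on which subscale definition applies: Protocol 11.3 assigns 7 and 6 items, SAP 7.2.1 and Appendix 14.3 assign 4 and 4.

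**The PERMP loss can also be small.** SKAMP items 9 to 11 rate completing work, accuracy and neatness, and PERMP is taken in the same sessions, so a correlation stronger than -0.3 is plausible. The math level is set by a pretest, which may narrow the spread between children and lower ρ. Hence the results for -0.5.

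**Stronger readings.** A reader might infer that the loss falls mainly on the 28 absolute Day 15 comparisons. That holds only under conditions on correlations that the documents do not give. A reader might also infer that standard errors could more than double. That needs ρ = 0.9, beyond the 0.84 reached in the hourly structure above. Nor does the absence of multiplicity adjustment make this worse: it concerns false positives, while this gap costs power.

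**Conclusion.** The gap is real and worth closing, but it is one of precision and clarity. Randomization keeps the treatment estimates unbiased, and the primary analysis uses its own baseline. The documents do not support a claim of bias, or of a deliberate departure from the protocol.

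The plan as written adjusts 58 of 73 secondary comparisons for another measure's baseline. For the 14 Day 15 PERMP comparisons the loss is moderate over the central range, about 10% to 34% or 0% to 21% in standard error depending on the SKAMP-PERMP correlation, and larger if ρ exceeds 0.7. For Day 15 subscale scores it is modest when k is near 0.9 and grows as k falls. For hourly PERMP change scores it is slight against the Day 1 mean and moderate against a time-matched value. Absolute Day 15 scores bear most of the loss only if the Day 1 to Day 15 correlation is moderate or higher, above about 0.4 to 0.5 depending on the benchmark, and higher still if SKAMP-CS and PERMP correlate strongly. Confidence in the literal reading and the counts is high; confidence in any single size is low.

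**What to change.** In SAP 7.5.2, state that each PERMP and SKAMP-subscale ANCOVA keeps treatment and site and replaces mean SKAMP-CS at baseline with the Day 1 (Visit 4) baseline of the same measure:
- the Day 1 seven-session mean, over available sessions, for day-mean endpoints and for absolute hourly Day 15 scores;
- the time-matched Day 1 value for hourly change scores. The Day 1 mean is an acceptable simpler choice there, with a standard error about 4% to 13% larger under the correlations assumed above.

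SKAMP-CS endpoints keep mean SKAMP-CS at baseline. If the table specifications already name the covariate, the SAP sentence should match them.

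The cost is one sentence before database lock and no new data. A child with no Day 1 value of a measure would drop out of that measure's Day 15 score analyses. Hourly change analyses lose no one further, because a child without the matched Day 1 value has no change score under any covariate. The absolute and change analyses at a given hour will still give different estimates, as they do now. Time-matched covariates for both would make them agree on the same children, but would raise the standard error of the absolute scores by about 10% to 12% over the four settings (for example sqrt(0.750/0.620) = 1.10 in the first).
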